8.6.8. Appropriateness of Measurements

The assessments, which will be made in this study are standard, and generally recognized as reliable, accurate, and relevant. Efficacy assessments are consistent with the WHO, COVID-19 Therapeutic Trial Synopsis.

9. ADVERSE EVENTS

9.1. Definitions

9.1.1. Adverse Event

An AE is defined in the ICH Guideline for GCP as “any untoward medical occurrence in a patient or clinical investigation subject administered a pharmaceutical product and that does not necessarily have a causal relationship with this treatment” (ICH E6:1.2).

Worsening of a pre-existing medical condition, (ie, diabetes, migraine headaches, gout) is to be considered an AE if there is either an increase in severity, frequency, or duration of the condition or an association with significantly worse outcomes.

Interventions for pretreatment conditions (ie, elective cosmetic surgery) or medical procedures that were planned before study enrollment are not considered AEs.

In the case of death, only record “Fatal” for the event causing death. AEs that are ongoing at the end of the study or time of death are to be noted as “continuing.”

The Investigator is responsible for reviewing laboratory test results and determining whether an abnormal value in an individual patient represents a significant change from baseline. In general, abnormal laboratory findings without clinical significance (based on the Investigator’s judgment) should not be recorded as AEs; however, laboratory value changes requiring therapy or adjustment in prior therapy are considered AEs.

9.1.2. Suspected Adverse Reaction

A suspected adverse reaction is any AE for which there is a reasonable possibility that the drug caused the AE. For the purposes of Investigational New Drug Application (IND) safety reporting, “reasonable possibility” and/or at least possibly related means there is evidence to suggest a causal relationship between the drug and the AE. A ‘suspected adverse reaction’ implies a lesser degree of certainty about causality than ‘adverse reaction’, which means any AE caused by a drug.

9.1.3. Serious Adverse Event

An AE or suspected adverse reaction is considered “serious” if, in the view of either the Investigator or Sponsor, it results in any of the following outcomes:

- is fatal.
For the purposes of this study, death due to SARS-CoV2 infection is not considered an SAE.
- is life-threatening (ie, places the patient at immediate risk of death).

- requires in-patient hospitalization (overnight stay) or prolongation of existing hospitalization.

As all patients are required to be hospitalized as inpatients to be eligible for this study, any event other than SARS-CoV2 infection requiring prolonging of inpatient hospitalization and/or rehospitalization after discharge will be considered an SAE. Hospitalization due to SARS-CoV2 infection is not considered an SAE, provided that it did not deteriorate in an unexpected manner during the study.

- results in persistent or significant disability/incapacity.
- is a congenital anomaly/birth defect.
- is an important medical event; an important medical event is an event that may not result in death, be life-threatening, or require hospitalization but may be considered an SAE when, based upon appropriate medical judgment, it may jeopardize the patient and may require medical or surgical intervention to prevent one of the outcomes listed in the definitions for SAEs. Examples of such medical events include allergic bronchospasm requiring intensive treatment in an emergency room or at home, blood dyscrasias or convulsions that do not result in inpatient hospitalization, or the development of drug dependency or drug abuse.

9.1.4. Unexpected Adverse Event

An AE or suspected adverse reaction is considered “unexpected” if it is not listed in the Investigator’s Brochure or is not listed at the specificity or intensity that has been previously observed; or, if an Investigator’s Brochure is not required or available, is not consistent with the risk information described in the General Investigational Plan or elsewhere in the current application, as amended.

9.1.5. Serious and Unexpected Suspected Adverse Reaction

A SUSAR is any event that meets all 3 of the following definitions:

- 1) suspected adverse reaction ([Section 9.1.2](#));
- 2) serious ([Section 9.1.3](#)); and
- 3) unexpected ([Section 9.1.4](#)).

9.2. Adverse Event Assessment

All AEs will be collected and recorded in this study from the time of initiation of study drug administration through the last visit for a patient. This includes AEs the patient reports spontaneously, those observed by the Investigator, and those elicited by the Investigator in response to open-ended questions during scheduled study center visits.

AEs that occur during or within 24 hours after study drug infusion are to be captured as individual signs and symptoms rather than a diagnosis of allergic reaction or IRR.

Each AE is to be assessed by the Investigator with regard to the following categories.

9.2.1. Serious/Non-Serious

AEs that meet the criteria specified in [Section 9.1.3](#) are to be considered serious.

9.2.2. Relationship to Study Drug

This determination is based on the Investigator's clinical judgment regarding the likelihood that the study drug caused the AE and may include consideration of some or all of the following factors:

- Alternative possible causes of the AE, including the patient's underlying disease or co-morbid conditions, other drugs, other host and environmental factors;
- The chronological relationship between the exposure to study drug and the AE;
- Whether the clinical or laboratory manifestations of the AE are consistent with known actions or toxicity of the study drug;
- Whether the AE resolved or improved with decreasing the dose or stopping the study drug (ie, dechallenge);

Whether the AE recurred or worsened with re-exposure to the drug (ie, rechallenge).

The relationship between the study drug and the AE will be described using one of the following categories [Table 2](#).

Table 2: Criteria for Determination of Adverse Event Relationship to Study Drug

Relationship	Definition
Related	The study drug is more likely the cause of the AE than other factors
Possibly Related	There is a reasonable possibility that the study drug is the cause of the AE, including that the study drug and another factor(s) are equally likely as causes of the AE
Unlikely Related	Another factor is considered more likely the cause of the AE than the study drug
Not related	Another factor is considered to be the cause of the AE

9.2.3. Relationship to SARS-CoV2 infection:

The relationship between each AE and SARS-CoV2 infection (related/unrelated) is to be documented.

9.2.4. Intensity

The intensity of each AE is to be assessed by the Investigator using the NCI CTCAE, version 5.0 (available at:

https://ctep.cancer.gov/protocolDevelopment/electronic_applications/docs/CTCAE_v5_Quick_Reference_8.5x11.pdf).

AEs not listed on the NCI CTCAE V5.0 are to be rated by the Investigator according to the categories in [Table 3](#).

Table 3: Criteria for Determination of Adverse Event Intensity

Intensity	Definition
Mild (Grade 1):	Asymptomatic or mild symptoms: clinical or diagnostic observations only; intervention not indicated.
Moderate (Grade 2)	Minimal, local, or non-invasive intervention indicated; limiting age-appropriate instrumental activities of daily living.
Severe (Grade 3):	Severe or medically significant but not immediately life threatening: hospitalization or prolongation of hospitalization indicated; disabling; limiting self-care activities of daily living; incapacitating with inability to work or perform normal daily activity.
Life-threatening (Grade 4):	Consequences: urgent intervention indicated.
Fatal (Grade 5)	AE resulted in death

9.2.5. Outcome

The outcome of each AE will be described using the categories in [Table 4](#).

Table 4: Criteria for Determination of Adverse Event Outcome

Outcome	Definition
Resolved without sequelae:	The event resolved and patient returned to baseline
Resolved with sequelae:	The event resolved but the patient is left with residual problems (eg, functional deficits, pain)
Resolving	At the last observation, the event was improving
Not Resolved	At the last observation, the event was unchanged
Death (Fatal)	To be used for the one AE which, in the judgment of the Investigator, was the primary cause of death
Unknown	There were no observations after the onset (initial observation or report) of the event

9.2.6. Study Drug Action

For each AE, the Investigator will indicate the action taken regarding the administration of study drug per the categories in [Table 5](#).

Table 5: Study Drug Action Taken as a Result of Adverse Events

Action	Definition
Discontinued (withdrawn)	Study drug was stopped permanently due to the AE
Dosing Interrupted	Study drug regimen was modified by being temporarily halted, but drug was not stopped permanently
Dose Decreased	Study drug regimen was modified by subtraction, ie, by decreasing the strength or amount
Dose Increased	Study drug regimen was modified by addition, ie, by increasing the strength or amount
None	No change in the administration of study drug

9.3. Recording Adverse Events

All AEs occurring from the time of initiation of study drug administration through the last follow-up visit, or after the end of the study, if thought to be related to study drug, are to be recorded in the source documents and in the eCRF. All AE reports are to contain the following details regarding the AE: a brief description, onset date and time, resolution date and time, intensity, treatment required, relationship to study drug, action taken with study drug, outcome, and whether the event is classified as serious.

AEs that occur during or within 24 hours after study drug injection should be captured as individual signs and symptoms (eg, dyspnea, rash, flushing) rather than a diagnosis of allergic reaction or IRR.

9.4. Reporting Serious Adverse Events

SAEs will be collected and recorded throughout the study period, beginning with the signing of the informed consent form (ICF) through the last follow-up visit, or after the end of the study if thought to be related to study drug.

The Investigator must report all SAEs within 24 hours of discovery to the Contract Research Organization (CRO) Safety Team.

SAE reporting, including supporting materials, will be performed by the study center personnel using a system approved by the Sponsor. Detailed training will be provided by the CRO. Contact information for guidance and assistance with SAE reporting is provided in the Study Reference Manual. A completed SAE report is to be entered into the system approved by the Sponsor within 24 hours of discovering the event. Upon entry into the system, the responsible parties (including Medical Monitor and Safety Reporting Specialist) will be immediately notified.

The Study Reference Manual will include an emergency back-up paper based reporting system, to be used if needed.

The CRO Safety Team will immediately (within one business day of receipt) forward the SAE report to the Sponsor. The initial report should include at least the following information:

- Patient's identification number;
- Description and date of the event;
- Criterion for serious; and
- Preliminary assignment of causality to study drug.

The Medical Monitor may contact the Investigator via telephone for urgent follow-up information regarding the SAE, as appropriate.

The Investigator, or designated party, should notify the appropriate IRB of SAEs occurring at the study center and other AE reports received from aTyr, in accordance with local procedures and statutes.

SAEs that are considered as possibly or definitely related to the investigational product, and as unexpected (ie, SUSARs), will be reported to the National Regulatory Authority(ies) and IRB by the Sponsor or Sponsor's designee as required by applicable local regulations. Per regulation, any fatal or life-threatening SUSAR will be reported to the National Regulatory Authority(ies)/IRB within 7 calendar days, and additional information within an additional 8 calendar days. The Sponsor or Sponsor's designee is required to submit any other SUSAR to the National Regulatory Authority(ies)/IRB within 15 calendar days of notification. The Sponsor or its designee is also responsible for notifying the investigational sites of all expedited SAEs, in

accordance with local requirements. The Investigator must keep copies of all expedited SAE information including correspondence with the Sponsor on file.

9.5. Follow-Up of Adverse Events

The Investigator must continue to follow all study drug-related TEAEs either until resolution or the Investigator assesses them as chronic or stable. This follow-up may extend after the end of the study and may be conducted by telephone contact or unscheduled visit.

9.6. Reporting Safety Information

The Investigator must promptly report to his or her IRB all unanticipated problems involving risks to patients, in accordance with local requirements. This may include death from any cause and all SAEs reasonably or possibly associated with the use of study drug according to the IRB's procedures.

9.7. Protocol Deviations Due to an Emergency or Adverse Event

Departures from the protocol will be determined as allowable on a case-by-case basis and only in the event of an emergency. The Investigator or other physician in attendance in such an emergency must contact the Medical Monitor as soon as possible to discuss the circumstances of the emergency.

The Medical Monitor, in conjunction with the Investigator, will decide whether the patient should continue to participate in the study. All protocol deviations and reasons for such deviations must be noted in the eCRF.

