6.4. Withdrawal and Replacement of Patients

6.4.1. Study Drug Discontinuation Criteria

Study drug administration must be permanently discontinued for a patient if any of the following events occur:

- A SAE that has a reasonable possibility of a causal relationship with the study drug.
- A severe IRR that includes cardiac and/or respiratory observations (see [Section 9.9](#) for Management of IRRs).
- Patient request to discontinue study drug dosing for any reason.
- Other findings that, at the discretion of the Investigator and/or Sponsor, indicate that study drug administration should be discontinued.

The Investigator has full discretion to stop study drug infusion at any time, if clinically warranted or in the patient's best interest.

All patients who have been dosed with any amount of study drug will continue to be followed for safety. Patients who discontinue study drug dosing at any time during the treatment period should return to the study center for the post treatment follow-up visits and as clinically indicated.

Patients who withdraw their consent will not receive any further study drug, but will be offered all follow-up safety assessments.

If a subject fails to attend scheduled study assessments, the Investigator must determine and document the reasons and the circumstances as completely and accurately as possible.

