6.4.2. Replacement of Patients

If a patient is withdrawn from the study for any reason, whether related to the study drug or not, or if a patient voluntarily withdraws before or after receiving the study drug, such patient will be considered an early-termination patient.

Investigator will make every effort to ensure that early-termination patients who have received study drug complete the safety follow up assessments.

Patients who are randomized and do not receive study drug will be replaced at the Sponsor's discretion. The decision regarding the replacement of patients will be documented.

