6.4.3. Study Withdrawal Criteria

Patients will be informed that they have the right to discontinue from the study and withdraw consent at any time for any reason, without prejudice to their medical care. The Investigator also has the right to withdraw patients from the study for any of the following reasons:

- Patient non-adherence to study drug or protocol requirements.
- Patient unwillingness to continue in the study.
- Any other reason, based upon the medical judgment of the Investigator.

The reason for study withdrawal is to be documented in the patient's source documents and electronic case report form (eCRF).

At the time of discontinuation from the study, patients are to have all the assessments planned for the final follow-up visit performed after the last study drug dose, if feasible.

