### 4.2 General Presentation Considerations

**Baseline:** the last available pre-treatment assessment, unless otherwise specify. All assessments should have time collected. If time is not collected and date of assessment is the same as study drug administration date then assessment will be assumed to be collected prior to treatment unless schedule of assessments and protocol indicate planned collection is always after dosing.

For baseline of oxygen use, total oxygen use in 24 hours before drug administration date.

**Day-of-Discharge (DoD):** day when patient is discharged from the hospital.

**Date of discharge:** date patient is discharged from the hospital.

**Early Termination (ET):** day when patient withdraws from the study before completion.

**End-of-Study (EOS):** the EOS assessment is at Day 60 for patients who complete the study.

**End of study date:** date of EOS assessment (Day 60) if patient completes the study or date of early withdrawal if patient discontinues early, or date of death.

**Study Day:** <Assessment Date> - study drug administration date + 1 if <Assessment Date> is on or after study drug administration date. <Assessment Date> - study drug administration date, if <Assessment Date> is before study drug administration date.

Durations are generally calculated as the stop date - start date +1, if not otherwise stated.

For elapsed time (eg, time since the initial diagnosis) is calculated as reference date - event date.

If more than one laboratory value is available for a given study day, the last valid observation will be used in summaries, unless otherwise stated. If it is not possible to determine which is the last measurement due to missing times, then the average of all measurements for that study day will be used as the value for that study day. All observations will be presented in listings.

Laboratory data will be presented in standard units.

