Days with fever up to Day 14 will be used as a sensitivity analysis. Days will be calculated the same as described for Days of supplemental oxygen (O2) up to Day 14.

Change from baseline in WHO Ordinal Scale score

The description of the WHO Ordinal Scale score is shown in [Section 6.2](#). The Number and percentage of patients on WHO Scale scores and change from baseline (-7, -6, -5, -4, -3, -1, 0, 1, 2, 3, 4) will be presented by visit. Shift table will be presented by visit as well.

Simple Ordinal logistic regression on the WHO Scale score at each visit (Days 5, 7, 14, 28, and 60) will be performed to compare ATYR1923 1 mg/kg versus Placebo and ATYR1923 3 mg/kg versus Placebo. Firth logistic regression ([Firth, 1993](#)) on the collapsed WHO Ordinal Scale (0-3 versus 4-8) at each visit (Days 5, 7, 14, 28, and 60) will be performed as well.

Distribution of WHO Ordinal Scale at 1, 2, 3, 4, 5, 6, 7, 10, 14, 28 and 60 days will be visualized by treatment group using an stacked bar chart. These figures will only consider scheduled assessments and in case the scheduled assessment is not available the mapped unscheduled TC follow up assessments as defined in [Section 4.2](#).

Time to Improvement in Clinical Status

Time to improvement in days is the time in which the patient sees a decrease after study treatment in the WHO Ordinal Scale score from baseline by at least 1 point, derived as:

date of decrease in WHO scale compared to baseline by at least 1 point - study drug administration date; or date of discharge from hospital - study drug administration date, whichever occurs first.

In the case that a patient has not decreased in the WHO scale or withdraws from the study, they will be censored at EOS date. Time to improvement will be analyzed using the Kaplan-Meier methods and Cox Proportional Hazards model as described in the above.

Repeat analysis above for improvement of WHO Ordinal Scale score by at least 2 points.

Additionally, time to improvement will be analyzed using an adapted derivation: date of decrease in WHO scale compared to baseline by at least 1 point - randomization date; or date of discharge from hospital - randomization date, whichever occurs first.

Related output will be noted as sensitivity analysis.

Time to improvement (by at least 1 and 2 points) will be analyzed based on mITT and EE Set. Sensitivity analysis for time to improvement will be analyzed based on mITT only.

*All-cause mortality*

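### After the single Day 1 dose a patient can be withdrawn at discretion with only safety follow-up promised, and the SAP then censors time to improvement at the withdrawal date

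*Protocol*

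**What the plan says.** **Routes out of the study.** Protocol 4.1 gives a one-day treatment period and 60 days of follow-up for all patients. Protocol 6.4.3 lets the Investigator withdraw a patient for "Patient non-adherence to study drug or protocol requirements" or for "Any other reason, based upon the medical judgment of the Investigator". Protocol 9.7 is narrower. It opens with "Departures from the protocol will be determined as allowable on a case-by-case basis and only in the event of an emergency" and continues "The Medical Monitor, in conjunction with the Investigator, will decide whether the patient should continue to participate in the study". It gives no criteria for that decision.

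**What continues after withdrawal.** Protocol 6.4.1 states "All patients who have been dosed with any amount of study drug will continue to be followed for safety". Protocol 6.4.2 states "Investigator will make every effort to ensure that early-termination patients who have received study drug complete the safety follow up assessments". Both speak of safety. Protocol 6.4.3 also asks for the final-visit assessments at discontinuation, if feasible, which is a single occasion.

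**What the SAP does.** SAP 4.2 sets the end of study date of a non-completer to "date of early withdrawal if patient discontinues early". In SAP 4.9.4.1, under Time to Improvement in Clinical Status, a patient who has not improved "or withdraws from the study, they will be censored at EOS date". Time to recovery is censored at the EOS visit, with no mention of withdrawal. Time to hospital discharge has rules for death in hospital and for patients still in hospital at EOS. It then refers to rules for discontinued patients without stating one.

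**The concern.** Withdrawal usually protects a patient from further exposure. Here there is none to avoid once the infusion is over, so withdrawal for anything other than the patient's own wish has only one effect on the analysis: outcomes stop being observed.

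Kaplan-Meier and Cox analyses assume that a censored patient has the same prospects as those still at risk. That fails if withdrawal follows a deviation prompted by worsening. A plausible path is a medication prohibited by Protocol 7.1.6.1 (immunosuppressants, or off-label drugs for SARS-CoV-2) given because the patient is failing. WHO score, oxygen use and discharge date are efficacy data and fall outside the safety follow-up that is promised. Recovery or improvement would be overstated, more so in the arm with more worsening, and the hazard ratio would be pulled toward 1.

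**Working it through.** The plan has no power, dropout or withdrawal figure to reproduce. The text was traced first, then the size was illustrated.

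**Step 1: which endpoints are censored at withdrawal?**

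| Endpoint (SAP 4.9.4.1) | Censoring rule given | Withdrawal |
|---|---|---|
| Time to improvement | EOS date | Named; EOS date is the withdrawal date by SAP 4.2 |
| Time to recovery | EOS visit | Not named; implied only if the EOS visit is read as the end of study date |
| Time to discharge | Death date, or EOS visit if still in hospital | No rule stated; implied at most |

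SAP 4.2 defines the EOS assessment as Day 60 for completers and defines the end of study date separately, so the last two rows are inference.

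**Step 2: Kaplan-Meier by hand.** From the documents: 30 patients, 1:1:1, so 30/3 = 10 per arm. Assumed: 6 of 10 recover on drug and 8 of 10 on placebo; all recoveries fall between Day 4 and Day 28; the others never recover; withdrawals occur on Day 4. With no censoring between the first and last recovery, the Day 28 estimate is recoveries divided by the number at risk after Day 4.

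| Non-recoverers withdrawn | Drug | Placebo |
|---|---|---|
| None | 6/10 = 60% | 8/10 = 80% |
| Half | 6/(10 − 2) = 75% | 8/(10 − 1) = 88.9% |
| All | 6/6 = 100% | 8/8 = 100% |

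Crude proportions over baseline N stay at 6/10 and 8/10 in every row.

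**Step 3: a second pattern, one arm of 10.** Assumed recovery days are taken in order from 3, 4, 5, 6, 7, 8, 10, 12, 14 and 20. Let k patients never recover and be withdrawn on Day 4, and let one further non-recoverer stay to Day 60. Two recoveries occur by Day 4, so 8/10 remain unrecovered. After the k withdrawals, 8 − k are at risk and all but one recover. The Day 28 estimate is 1 − 0.8/(8 − k).

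| k | Kept at risk | Censored on Day 4 |
|---|---|---|
| 1 | 80% | 1 − 0.8/7 = 88.6% |
| 2 | 70% | 1 − 0.8/6 = 86.7% |
| 3 | 60% | 1 − 0.8/5 = 84.0% |

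Without the extra non-recoverer the figures are 90%, 80% and 70%, against 100% each time. The rise is therefore about 9 to 30 percentage points.

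**Step 4: hazard ratio for recovery, drug v placebo, by simulation.** Assumed: 20,000 per arm; lognormal recovery time with median 7 days and log-SD 0.5; 40% v 20% never recover; withdrawal on Day 4. The ratio is about 0.61 with none withdrawn, 0.69 with half and 0.95 with all. Repeat runs gave 0.60 to 0.61, 0.68 to 0.69 and 0.94 to 0.97. With a quarter withdrawn it is about 0.64.

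**The case against.** A reader might infer that Protocol 9.7 makes deterioration a ground for removal. It does not: its trigger is an emergency departure from the protocol. Protocol 4.1.1 keeps intubated patients in the study, with WHO scores still collected and Day 28 and Day 60 contacts. Protocol 7.1.6.1 allows other medications, including remdesivir, and nothing says that use of a prohibited one ends participation. SAP 4.6.2 summarises major deviations within the mITT set, so patients with deviations are expected to be analysed. All of this stands. The path from worsening to withdrawal is possible under the text, not prescribed by it.

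The SAP also has safeguards. SAP 4.3.1 keeps every patient in the denominator of proportion endpoints, including recovery by Day 14 and Day 28. SAP 4.9.4 reports crude event proportions over baseline N beside the Kaplan-Meier estimates. Oxygen and fever days have a Day 14 sensitivity analysis that scales up withdrawals. The primary TEAE endpoint is largely protected by the safety follow-up. These points stand, but none of them covers the Kaplan-Meier estimates or hazard ratios.

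Blinding of Investigator and Sponsor argues against selective removal by arm. It does not remove the problem, because the example applies one rule to both arms and the distortion comes from unequal worsening.

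Finally, sampling error is far larger. In the Step 4 model with 10 per arm and no withdrawals, the central 95% of hazard ratios runs from about 0.18 to 1.74.

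**Conclusion.** The point holds in a limited form. The text permits discretionary withdrawal after the only dose, promises only safety follow-up afterwards, and has an express rule that censors time to improvement at withdrawal. For recovery and discharge the same handling is implied, and the missing rule is itself a gap. Protocol 6.4.3 is the wider route and 9.7 the narrower.

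The size depends on assumptions. With half of the non-recoverers withdrawn on Day 4, Day 28 recovery moves from 60% v 80% to 75% v 89% and the hazard ratio from about 0.61 to about 0.69. No withdrawal rate is documented, and nothing shows that any such withdrawal occurred.

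Two stronger conclusions are not supported. One is that the bias would reverse the hazard ratio: under a common rule it stays below 1 even with all non-recoverers withdrawn, and the drug still looks worse with half withdrawn. The other is that one or two withdrawals decide the trial's result: Protocol 10.1.3 reports no power calculation, and SAP 4.9.2 treats all comparisons as exploratory. The change is worth making because it is cheap and removes an avoidable source of informative censoring.

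**What to change.** **Protocol 6.4.3 and 9.7.** State that after dosing a protocol deviation is recorded but does not by itself end participation. State also that any patient withdrawn after dosing, for a reason other than withdrawal of consent, still has WHO score, oxygen use, discharge date, AEs and vital status collected to Day 60. The second sentence must cover the medical-judgment route in 6.4.3 as well as deviations.

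**SAP 4.2 and 4.9.4.1.** Use these later data for time to improvement, recovery and discharge. Censor only at the last date with known status, and write out the withdrawal rule for recovery and discharge. Censoring at last known status can still be informative, so complete collection to Day 60 does most of the work.

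**Labelling.** The SAP revision history shows that versions 2.0 and 3.0 were modified after unblinding. Any SAP change made now should be labelled post hoc.

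**Cost.** A few sentences in each document, and some extra chart review and telephone contact. The estimates will then include the effect of treatments given after dosing, which the report should say.
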